## FUNDING/SUPPORT

0 unresolved  
comment(s)

If the research is being submitted to, supported by, or conducted in cooperation with an external or internal agency or funding program, indicate below all the categories that apply. 

Not applicable

## Check All That Apply

- Grant application pending
- (HHS) Dept. of Health & Human Services
  - (NIH) National Institutes of Health
  - (CDC) Centers for Disease Control & Prevention
    - (HRSA) Health Resources and Services Administration
    - (SAMHSA) Substance Abuse and Mental Health Services Administration
  - (DoJ) Department of Justice or Bureau of Prisons
  - (DoE) Department of Energy
  - (EPA) Environmental Protection Agency
- Federal Agencies Other Than Those Listed Here
  - Industry (Other than Pharmaceutical Companies)
  - Internal Grant Program w/ proposal
  - Internal Grant Program w/o proposal
  - National Science Foundation
  - Other Institutions of Higher Education
  - Pharmaceutical Company
  - Private Foundation/Association
  - U.S. Department of Education
  - State

## Other:

Appalachian Regional Commission

Click applicable listing(s) for additional requirements and information:

- [\(HHS\) Dept. of Health & Human Services](#)
- [\(NIH\) National Institutes of Health](#)
- [\(CDC\) Centers for Disease Control & Prevention](#)
- [\(HRSA\) Health Resources & Services Administration](#)
- [\(SAMHSA\) Substance Abuse & Mental Health Services Administration](#)
- Industry (Other than Pharmaceutical Companies) [[IRB Fee Info](#)]
- [National Science Foundation](#)
- [\(DoEd\) U.S. Department of Education](#)
- [\(DoJ\) Department of Justice or Bureau of Prisons](#)
- [\(DoE\) Department of Energy Summary and \[Department of Energy Identifiable Information Compliance Checklist\]\(#\)](#)
- [\(EPA\) Environmental Protection Agency](#)

Specify the funding source and/or cooperating organization(s) (e.g., National Cancer Institute, Ford Foundation, Eli Lilly & Company, South Western Oncology Group, Bureau of Prisons, etc.):

The project is biphasic in design, as required by the NIH UG3/UH3 funding structure, with a 2-year assessment phase (UG3) followed by a 3-year intervention phase (UH3) that is informed by results of the assessment. The UG3 phase began in August 2017 and is described in the approved IRB protocol # 43520. The current IRB protocol covers the 3-year UH3 phase which begins August 1, 2019. UH3 funding is with the National Institute on Drug Abuse. The initiative is co-funded by NIH, CDC, SAMHSA, and the Appalachian Regional Commission.

Add Related Grants

If applicable, please search for and select the OSPA Account number or Electronic Internal Approval Form (eIAF) # (notif #) associated with this IRB application using the "Add Related Grants" button.  
If required by your funding agency, upload your grant using the "Grant/Contract Attachments" button.

[Add Related Grants](#)

[Grant/Contract Attachments](#)

The research involves use of Department of Defense (DoD) funding, military personnel, DoD facilities, or other DoD resources.  
(See [DoD SOP](#) and [DoD Summary](#) for details)

Yes  No

Using the "attachments" button (below), attach applicable materials addressing the specific processes described in the DoD SOP.

[DOD SOP Attachments](#)

Additional Certification: (If your project is federally funded, your funding agency may request an Assurance/ Certification/Declaration of Exemption form.) Check the following if needed:

Protection of Human Subjects Assurance/Certification/Declaration of Exemption (Formerly Optional Form – 310)

[Assurance/Certification Attachments](#)

## OTHER REVIEW COMMITTEES

0 unresolved  
comment(s)

If you check any of the below committees, additional materials may be required with your application submission.

Does your research fall under the purview of any of the other review committees listed below? [If yes, check all that apply and attach applicable materials using the attachment button at the bottom of your screen.]

Yes  No

**Additional Information**

Institutional Biosafety Committee  
 Radiation Safety Committee  
 Radioactive Drug Research Committee  
 Markey Cancer Center (MCC) Protocol Review and Monitoring Committee (PRMC)  
 Graduate Medical Education Committee (GME)  
 Office of Medical Education (OME)

- [Institutional Biosafety Committee \(IBC\)](#) - Attach required IBC materials
- [Radiation Safety Committee \(RSC\)](#) - For applicability, see instructions and attach form
- [Radioactive Drug Research Committee \(RDRC\)](#)
- [Markey Cancer Center \(MCC\) Protocol Review and Monitoring Committee \(PRMC\)\\*\\*](#) - Attach MCC PRMC materials, if any, per instructions
- [Office of Medical Education \(OME\)](#)
- [Graduate Medical Education Committee \(GME\)](#)

**Attachments**

**\*\* If your study involves cancer research, be sure to select "Cancer Research" in the "Research Attributes" section.** ORI will send your research protocol to the Markey Cancer Center (MCC) Protocol Review and Monitoring Committee (PRMC). The [MCC PRMC](#) is responsible for determining whether the study meets the National Cancer Institute (NCI) definition of a clinical trial and for issuing documentation to you (the investigator) which confirms either that PRMC approval has been obtained or that PRMC review is not required. Your IRB application will be processed and reviewed independently from the PRMC review.

Section 18 Page 1 of 1

## ADDITIONAL INFORMATION/MATERIALS

0 unresolved  
comment(s)

Do you want specific information inserted into your approval letter?  Yes  No

## Approval Letter Details:

If you wish to have specific language included in your approval letter (e.g., serial #, internal tracking identifier, etc...), type that language in the box below exactly as it should appear in the letter. The text you enter will automatically appear at the top of all approval letters, identical to how you typed it, until you update it. Don't include instructions or questions to ORI staff as those will appear in your approval letter. **If these details need to be changed for any reason, you are responsible for updating the content of this field.**

## Additional Materials:

If you have other materials you would like to include for the IRB's consideration, check all that apply and attach the corresponding documents using the Attachments button below.

Detailed protocol  
 Dept. of Health & Human Services (DHHS) approved protocol (such as NIH sponsored Cooperative Group Clinical Trial)  
 Other Documents

## Protocol/Other Attachments

Attach Type	File Name
Other	Summary of Adverse and Serious Adverse Events.pdf
Other	Modification Request Memo 092123.pdf

NOTE: [Instructions for Dept. of Health & Human Services \(DHHS\)-approved protocol](#)

If you have password protected documents, that feature should be disabled prior to uploading to ensure access for IRB review.

To view the materials currently attached to your application, click "All Attachments" on the left menu bar.

## Statistical Design and Power

We will explore intervention effects on PWUD using: (1) longitudinal quantitative data from START-C2H participants; and (2) qualitative data with PWUD START-C2H participants about the intervention's perceived effectiveness, and the perceived pathways through which it operates.

### Exploratory Quantitative Analysis of START-C2H survey data:

Our community randomized trial consists of clustered data with participants nested within counties. To account for this "doubly-repeated" measures design, we will analyze all results using generalized linear mixed models. The covariance matrix for all observations within a county may be written as the Kronecker product of the compound symmetric covariance matrix for participants nested within county and a 2 by 2 residual covariance matrix for repeated measures nested within participants. Implementing the covariance model can be done in both PROC MIXED (for continuous measures) and PROC GLIMMIX (for categorical measures) in SAS by specifying a random intercept for county, and a compound symmetric residual matrix across time (repeated measures within participant). To estimate change in our primary outcomes due to the intervention we will begin by analyzing models of the following form:  $g(y) = \beta_0 + \beta_1 Time + \beta_2 Int + \beta_3 Time * Int$  where  $g()$  represents the appropriate link function for outcome  $y$ ,  $Time$  is a pre-post indicator variable, and  $Int$  is an indicator for the intervention group. The parameter of primary interest is  $\beta_3$ , the difference in slope between the intervention and control group. While our primary outcomes can be approximated as normally distributed, the link function  $g()$  will be modified as necessary to properly model the distribution for each outcome.

**Missing Data.** We will use multiple imputation to account for non-response over time and potential attrition. Additional augmentation variables found to be predictive of missingness will also be included in the imputation model. Ten imputations will be implemented. Additionally, we will use multiple imputation by chained equations to allow for imputation of non-normally distributed variables. All imputation analyses will be done using PROC MI and PROC MIANALYZE in SAS.

**Power.** We estimated the statistical power to preliminarily detect a change in our outcomes using PROC GLMPOWER in SAS v9.4., accounting for autocorrelation within participants and nesting within counties. We estimate power for a multivariate model equivalent to our planned repeated measures models previously described. Because these analyses are exploratory (due to the smaller-than-anticipated sample size), we set the alpha to 0.10. Based on existing data, we assume a within-county ICC of 0.05 and a within-person autocorrelation of 0.35. We estimate power for all outcomes as approximately Gaussian. We further assume a type-1 error rate of 0.10, 12 counties, and 20 participants per county. At these sample sizes and with an exploratory p-value=0.10, we achieve statistical power of 0.80 for standardized mean of 0.55, or moderate sized effects with an alpha=0.10.

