#### COVID-19 Policies

We are changing the trial duration from three years to two years. To accommodate this shorter time period, we are modifying the study design from a stepped-wedge trial to a case crossover trial. We will randomize the 12 counties to two groups of six counties each versus three groups of four counties each. All counties will start at the same time. During months 1-6, counties randomized into Group 1 will receive the intervention, while counties randomized to Group 2 will serve as the comparison group. In Months 7-12, Group 1 counties will shift to the comparison group, and Group 2 counties will receive the intervention. In Months 13-18 we will conduct follow-up assessments in all counties. Months 19-24 will be devoted to data analysis and dissemination of the findings.

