laptop and access to the electronic screener during any recruitment event. Staff will then follow-up with the individuals to let them know if they are potentially eligible/not eligible; if eligible, staff will ask if the individual would like to complete the screener. Interested individuals may also complete the pre-screening survey themselves if preferred due to limited time, share with staff, who will then follow-up with them to let them know if they are potentially eligible/not eligible; if eligible, staff will ask if the individual would like to complete the screener. Staff will store completed paper screeners in a lock box and then in a locked filing cabinet in their field office upon return.

Once we enroll 15 individuals in a county, we will place a hold on additional recruitment efforts for that county; however, we will resume recruitment again when all intervention counties are switched to control and all control counties are switched to intervention per our study design (cross-over trial).

6/28/22 Modification - Study staff will contact participants currently enrolled in comparison counties and offer them enrollment in the intervention group.

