#### Comparison Condition

We will initiate the comparison group in each county six months before the intervention begins. The current "treatment as usual" condition for most individuals, especially individuals not entering parole/probation supervision, is to provide no post-release services. Given the high risk of overdose post-release, we will conduct a pre-release overdose intervention with the comparison cohort. Individuals recruited in the community will receive overdose education during their baseline visit as well. Overdoses are not a primary study outcome, and it would be unethical to withhold overdose education from this cohort. Six months before the intervention starts in a county, REHNS will use the same pre-release recruitment, consent, and enrollment protocols (including eligibility criteria, except individuals must live in counties that are currently randomized to the comparison group) as proposed for the intervention condition. As with START's original evaluation, we will administer a single session, pre-release intervention for the comparison group; if someone is recruited in the community, they will receive this visit as well. Specifically, the comparison group participants will complete the a training with people demonstrating how to respond to an overdose and narration on preventing, recognizing, and responding effectively to an opioid OD, accompanied by information about Kentucky's Good Samaritan Law and Naloxone Access Law. REHNS will answer questions after the video. Individuals will receive a Community Resource Guide at this visit.

As in the intervention group, comparison group participants will complete assessments at pre-release (two sessions), for those recruited in the community this will happen at the REHNS office, and at 3 months and 6 months weeks post-release (post-enrollment for those recruited in the community). Surveys will be identical to those delivered to the intervention cohort, as will incentives. No interventions will be delivered at these follow up appointments. Retention efforts for comparison participants will be identical to those for intervention participants (described previously).

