Triangulating across qualitative and quantitative findings: We will use joint displays to systematically compare and contrast qualitative and quantitative findings for each intervention component/outcome relationship (e.g., preliminary [i.e.,  $p < 0.10$ ] hypothesis test results about the relationship of receiving FTS to subsequent overdose vs. qualitative grounded theory about this same relationship). When qualitative and quantitative findings both suggest an ameliorative relationship, we will conclude that the available evidence supports a beneficial effect. When both find an adverse relationship, we will conclude that the evidence indicates a harmful effect. When neither suggests a relationship, we will conclude that the evidence indicates no effect. When quantitative and qualitative results diverge, we will return to the qualitative and quantitative data to learn if we can resolve this discrepancy. Qualitative data may illuminate an unexpected confounder for the quantitative hypothesis test. Alternatively, qualitative data may suggest that the intervention only has an effect in one subgroup (e.g., individuals residing in counties with more services) and the quantitative findings reach a null conclusion because the quantitative sample is small, and includes both people who do and do not live in such counties. We will seek to systematically explore all divergences using these tables, and seek to refine relational statements and grounded theories accordingly. We will rely solely on qualitative data to learn whether the intervention effect is attenuated in a subgroup (e.g., women), given that the quantitative sample is underpowered to detect effect moderation.

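### The SAS model named in the SAP is not the Kronecker covariance it is said to implement; separately, the stated power (0.80 at 0.55) matches neither that model nor the two-period county crossover

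*Combined protocol and SAP*

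**What the plan says.** In the SAP, under Exploratory Quantitative Analysis of START-C2H survey data, the covariance of a county's observations "may be written as the Kronecker product of the compound symmetric covariance matrix for participants nested within county and a 2 by 2 residual" block for the two time points. The same paragraph says this can be fitted in PROC MIXED or PROC GLIMMIX "by specifying a random intercept for county, and a compound symmetric residual matrix across time (repeated measures within participant". The model has Time, Int and Time*Int. The last coefficient, β3, is the parameter of primary interest. There is no period term.

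The Power paragraph takes ICC 0.05, autocorrelation 0.35, alpha 0.10, 12 counties and 20 participants per county. It says "We estimate power for a multivariate model equivalent to our planned repeated measures models previously described", and that "we achieve statistical power of 0.80 for standardized mean of 0.55". It does not give the split of the 20 between conditions, the sidedness or the df.

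The protocol's Study Design section (COVID-19 Policies) now has two groups of six counties that swap conditions: "In Months 7-12, Group 1 counties will shift to the comparison group, and Group 2 counties will receive the intervention". The recruitment section holds enrolment at 15 per county until "all intervention counties are switched to control and all control counties are switched to intervention per our study design (cross-over trial". The Comparison Condition section still says "We will initiate the comparison group in each county six months before the intervention begins".

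**The concern.** There are two separate problems. First, the SAS sentence does not deliver the covariance described just before it, and the difference falls on β3. A test presented as adjusted for county clustering would contain no clustering of change. Second, the power figure appears to belong to a layout in which each county stays in one condition, whereas every county now serves in both.

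What is at stake is the SE of the primary parameter and the reader's idea of what the trial can detect. Both feed the conclusions. Under Triangulating across qualitative and quantitative findings, the SAP says "When qualitative and quantitative findings both suggest an ameliorative relationship, we will conclude that the available evidence supports a beneficial effect". It draws a matching conclusion of harm when both are adverse, and of no effect when neither shows a relationship. The quantitative side of that rule is a test at p<0.10.

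**Working it through.** **Inputs.** From the Power paragraph: ICC 0.05, within-person correlation 0.35, alpha 0.10, 12 counties, 20 per county, effect 0.55 (taken in outcome SD units, total variance 1). From the protocol: six plus six counties, and a hold at 15 per county in each period. Inferred or assumed: two-sided test, 10 df (12 − 2), identity link, complete pairs, and an even split of the 20 into 10 per county-period.

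**1. The two covariances, for different people in one county.**
- Kronecker: same time 0.05; different times 0.05 × 0.35 = 0.0175.
- Random intercept plus compound-symmetric residual: 0.05 at the same time and 0.05 at different times.
- They agree only if the ICC is 0 or the autocorrelation is 1.

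**2. Reproducing the stated power.** Var(change) = 2(1 − 0.35) = 1.30. Under the Kronecker form the change scores also have ICC 0.05, so the design effect is 1 + 19 × 0.05 = 1.95. With each county in one arm:

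SE(β3) = √(1.30 × 1.95/20 × 2/6) = 0.2055; noncentrality 0.55/0.2055 = 2.676.

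Two-sided power at alpha 0.10 is 0.801 on 10 df, and the effect with 0.80 power is 0.55. Other df fit less well (0.828 on 22 df, 0.849 normal).

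**3. The named SAS model.** The county intercept is the same before and after, so it cancels from the change:

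SE(β3) = √(1.30 × 2/120) = 0.1472.

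Generalised least squares gives this value whatever county variance is used, in either layout. Power at 0.55 is 0.966 (10 df) to 0.981 (238 df). The effect with 0.80 power is 0.394 to 0.367.

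**4. The crossover.** Let m be the number per county-period and s the share of the county correlation of change that is specific to one period. The documents give no value for s, so the full range is shown:

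Var(β3) = [2 × 0.05 × 1.30 × s + 2 × 0.95 × 1.30/m]/12.

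| s | SE, m = 10 | Power at 0.55, m = 10 (10 df) | Detectable effect, m = 10 | Detectable effect, m = 15 |
|---|---|---|---|---|
| 0 | 0.1435 | 0.97 | 0.38 | 0.31 |
| 0.5 | 0.1612 | 0.94 | 0.43 | 0.37 |
| 1 | 0.1772 | 0.89 | 0.47 | 0.42 |

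No case gives 0.80 at 0.55.

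**5. Type I error of the named test in the crossover.** The ratio of true to reported variance is 0.95 + 0.05ms. With critical value c, type I error is 2(1 − Φ(c/√ratio)). For m = 10:

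| s | Ratio | c = 1.645 (large df) | c = 1.812 (t on 10 df) |
|---|---|---|---|
| 0 | 0.95 | 0.091 | 0.063 |
| 0.1 | 1.00 | 0.100 | 0.070 |
| 0.2 | 1.05 | 0.108 | 0.077 |
| 0.5 | 1.20 | 0.133 | 0.098 |
| 1 | 1.45 | 0.172 | 0.132 |

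The level is exactly 0.10 when s = [(c/1.645)² − 0.95]/(0.05m). That is about 10% with large df and about 53% with t on 10 df. With m = 15 and large df it is 0.05/0.75, about 7%. The SAP names no df method.

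**The case against.** The strongest reply is that little harm follows under the documents' own assumptions. If the Kronecker form is taken literally in the crossover (s = 0), the true SE is 0.1435 and the named model reports 0.1472, about 2.6% too large and so conservative. County correlation shared across periods largely cancels in a within-county comparison anyway. The stated power lies below every alternative computed, the analysis is labelled exploratory, and the model is described as a starting form. The GLMPOWER inputs are not shown, and 0.80 does match one of the two covariance descriptions in the SAP.

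Most of this stands, and it limits the point. It does not remove it. The SAP calls the SAS statement an implementation of the Kronecker form, which it is not, and calls the power model equivalent to the planned analysis. Attrition does not bridge the gap: with N participants left the named model has SE √(5.2/N), and its power falls to 0.80 only at about 108 (residual df) to 123 (10 df) of the 240.

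A reader might infer three stronger things:
- **That 0.80 is an arithmetic slip.** It is not; step 2 reproduces it.
- **That the trial is underpowered.** Every alternative gives more power than stated.
- **That the test is shown to be anti-conservative.** A type I error of about 0.24 would follow if each county stayed in one arm, the Kronecker form held and the named model were fitted with large df. The current design is a crossover, and there the direction depends on s and the df method, neither of which the documents give.

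**Conclusion.** The point holds as two distinct errors of specification. The named SAS model is not the stated covariance, and it leaves county clustering of change out of the test of β3. This is exact for an identity link with complete pairs and approximate for other links. The power statement fits the Kronecker form with one condition per county. It does not fit the named model (power 0.97 to 0.98, detectable effect 0.37 to 0.39). Because of layout rather than covariance, it does not fit the crossover either (0.38 to 0.47 with 10 per county-period, 0.31 to 0.42 with 15; 10 df). The stated detectable effect of 0.55 is conservative but wrong for the model and the design.

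Type I inflation is a risk only: with 10 per county-period it runs from 0.091 to 0.172 with large df and from 0.063 to 0.132 with a t(10) critical value. These ranges rest on the assumed split and the full range of period-specific share. The plan should be corrected, since the text is wrong as written and the change is cheap.

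**What to change.** - **Implementation sentence.** Rewrite it so that β3 is tested against county-level variation in change in the crossover, with period terms and a stated df method.
- **Approximately normal outcomes.** Compare each county's period-1 minus period-2 mean change between the two sequence groups (10 df). Run it within each imputation and pool with complete-data df of 10. This allows for period effects. In simulated normal data its type I error stayed at 0.098 to 0.102 over the full range of period-specific share, and at 0.098 to 0.101 with cell sizes from 4 to 16.
- **Categorical outcomes.** Use county-level differences in proportions, or a GLIMMIX model with county-by-time terms whose type I error has been checked first. The check matters: even for balanced normal data, a mixed model with county-by-time and county-by-period-by-time effects drifted from 0.075 to 0.113 when variances were bounded at zero.
- **Power paragraph.** State the number per county-period, the sidedness and the df. Restate power for the crossover and the model actually fitted, over a range of period-specific share.
- **Design text.** Reconcile the Comparison Condition section (comparison first in each county) with the Study Design section (Group 1 starts on intervention). If the comparison came first everywhere, condition and period would be confounded and there would be no sequence groups to compare.

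The cost is SAP wording, a few lines of SAS and a rerun of the power calculation, with no new data. The test has fewer df: with 10 per county-period the average 90% half-width for β3 is about 0.25 to 0.31, against 0.24 from the named model. The fix does not address carry-over between periods.

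### The primary contrast is an unadjusted difference in pre-post change; a baseline-adjusted model should be prespecified beside it (variance cut at most about a third, often less), with one covariance structure and power restated for the crossover

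*Combined protocol and SAP*

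**What the plan says.** The section Exploratory Quantitative Analysis of START-C2H survey data gives a model with an intercept, Time (a pre/post indicator), Int and their product. The coefficient to be interpreted is the product term β3, "the difference in slope between the intervention and control group". The model is introduced as a starting point: "we will begin by analyzing models of the following form". No baseline-adjusted model is named there or elsewhere in Statistical Design and Power.

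The same section describes the covariance twice. It is first a Kronecker product of a between-participant compound-symmetric matrix and a 2 by 2 within-participant matrix. It is then a SAS implementation obtained by "specifying a random intercept for county, and a compound symmetric residual matrix across time".

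The Power paragraph states: "we assume a within-county ICC of 0.05 and a within-person autocorrelation of 0.35". It takes 12 counties with 20 participants each and reports power 0.80 at a standardized effect of 0.55. On the significance level it says: "Because these analyses are exploratory (due to the smaller-than-anticipated sample size), we set the alpha to 0.10".

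Under Study Design, COVID-19 Policies, the trial is now a two-period county crossover: at month 7 "Group 1 counties will shift to the comparison group, and Group 2 counties will receive the intervention". Baseline exists in both arms; on the comparison arm's assessments, Comparison Condition says "Surveys will be identical to those delivered to the intervention cohort". The same section shows that recruitment follows county allocation, since eligibility is the same "except individuals must live in counties that are currently randomized to the comparison group".

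**The concern.** Because Int has its own coefficient, the baseline means of the two arms are free to differ, and for a Gaussian outcome β3 is the difference in mean change scores. At a within-person correlation of 0.35, subtracting the whole baseline adds more noise than it removes: a change score has variance 1.30σ², more than the 1.00σ² of the follow-up value alone. Regressing on baseline uses the same information with a better weight.

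The plan relaxed its alpha because the sample fell short (12 × 20 = 240 in the Power paragraph, against 1200 under Study Population). Under Triangulating across qualitative and quantitative findings, results at p<0.10 help decide between benefit, harm and no effect. Precision given up in the main contrast therefore carries into the conclusions.

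**Working it through.** **Inputs from the Power paragraph:** 12 counties × 20, ICC 0.05, ρ = 0.35, alpha 0.10, Gaussian outcome. **Assumed:** 120 per condition, two-sided test, 10 df, outcome SD of 1 and, except in step 5, complete data and equal pre and post variances.

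**1. The stated power.** Treat counties as parallel arms under the Kronecker covariance.
- Design effect: 1 + 19 × 0.05 = 1.95.
- Variance of β3: 2 × 2(1 − 0.35) × 1.95/120 = 0.04225, so SE 0.2055.
- Noncentral t with 10 df: power at 0.55 is 0.801, against the stated 0.80 (0.805 with 11 df).

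Other variants miss it: normal approximation 0.849, 238 df 0.847, one-sided normal 0.918, follow-up value only 0.883. In the same parallel layout, the SAS form gives variance 2 × 1.30/120 = 0.02167 and power 0.966. The two covariance descriptions are therefore not interchangeable.

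**2. Effect of the baseline covariate, per person.** Change score: 2(1 − ρ) = 1.30. Baseline-adjusted: 1 − ρ² = 0.8775. Cut: 1 − 0.8775/1.30 = 32.5%.

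In the layout of step 1, SE falls from 0.2055 to 0.1689, the effect detectable with 80% power from 0.55 to 0.451, and power at 0.55 rises from 0.801 to 0.916.

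**3. Crossover with a stable county effect** (10 per county-period, period term).
- Kronecker: 2 × 1.30 × 0.95/120 = 0.02058 falls to 2 × 0.8775 × 0.95/120 = 0.01389, a cut of 32.5%. Detectable effect 0.384 to 0.315.
- SAS form: residual variance 0.95, pre-post covariance 0.35 − 0.05 = 0.30, within-county correlation 0.30/0.95 = 0.316. Variance 2 × 0.95 × 2(1 − 0.316)/120 = 0.02167 falls to 2 × 0.95 × (1 − 0.316²)/120 = 0.01425, a cut of 34.2%. Detectable effect 0.394 to 0.319.

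**4. Where the county effect removes the gain (SAS form).** A change score cancels a county effect that is constant from pre to post. The adjusted estimate leaves a share (1 − slope) of it.
- Crossover, county effects unrelated between periods (assumed): 0.01425 + 2 × 0.684² × 0.05/12 = 0.01816, against 0.02167. The cut is 16%, or 18% with slope 0.35. At a between-period county correlation of 0.5 it is 25-26%.
- Parallel counties: 0.01425 + 2 × 0.684² × 0.05/6 = 0.02206, against 0.02167. The change is −2% with this slope and +2% with slope 0.35, so about nil.

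**5. Relaxing the other assumptions.**

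*Attrition.* The plan imputes missing values, so participants with only a baseline still inform β3. With a proportion r retained and data missing at random, the per-person variance is (1 − ρ²)/r + (1 − ρ)² unadjusted and (1 − ρ²)/r adjusted. The documents give no retention rate, so r is assumed. Results for the stable-county crossover:

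| r | Cut, ρ = 0.35 | Cut, ρ = 0.316 |
|---|---|---|
| 1.0 | 32.5% | 34.2% |
| 0.8 | 27.8% | 29.4% |
| 0.7 | 25.2% | 26.7% |
| 0.5 | 19.4% | 20.6% |

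*Unequal variance.* With k the ratio of follow-up to baseline SD (assumed range), change has variance 1 + k² − 0.7k and the adjusted value 0.8775k². At k = 1.3 this is 1.780 against 1.483 (17%); at k = 0.7 it is 1.000 against 0.430 (57%).

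**6. Price in bias.** Suppose the arms differ at baseline by δ.
- If δ would have persisted unchanged without treatment, β3 is unbiased and the adjusted estimate is off by (1 − 0.35)δ = 0.65δ. In the stable-county crossover its mean-squared-error advantage is gone at δ = √(0.02058 − 0.01389)/0.65 = 0.126 SD, about 0.13. That is one standard error of the baseline difference: √(2 × 0.95/120) = 0.126.
- If δ would not have persisted, β3 is off by the full δ and the adjusted estimate by 0.35δ.

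**The case against.** The strongest counter-argument is that a difference in change is a defensible choice when recruitment follows allocation. Staff and participants can know the county's condition. One flyer highlights the intervention (Subject Recruitment Methods & Advertising, COVID-19 Policies), and earlier control enrolees in four counties became eligible for the intervention (Recruitment via existing study cohorts). With a persistent baseline difference of 0.2 SD, the adjusted estimate would be biased by 0.65 × 0.2 = 0.13. At SE 0.118 and 10 df, the nominal 10% test would then reject a true null about 27% of the time. The trial could not reliably detect an imbalance of that order. This stands, and it rules out simply replacing β3. It does not make β3 safe, because a difference that fades biases β3 more. The documents do not say which case applies.

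The second argument is that a gain of a third is a best case. It also stands. Attrition shrinks the gain. Entry criteria that require recent opioid use or injection may narrow the baseline spread, and recall windows change at follow-up (Survey content), so a follow-up SD above the baseline SD is plausible. The primary outcomes are not named in the analysis section, so the size cannot be settled.

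Third, the model is only where the team will begin, so adjustment is not excluded. True, but nothing is named, and choosing between two estimators after seeing data is the discretion a plan should remove.

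**Conclusion.** The point holds as an efficiency recommendation for an exploratory analysis. The primary contrast is an unadjusted difference in change, and baseline is already collected in both arms. The variance cut from a baseline covariate is at most about a third (32.5-34%) under ρ = 0.35, equal variances and complete data, with either the Kronecker covariance or a crossover with a stable county effect. It falls to 28-29%, 25-27% and 19-21% at assumed retention of 80%, 70% and 50%, to about 17% at an SD ratio of 1.3, to 16-18% with county effects that vary fully by period under the SAS form, and to about nil for parallel counties under that form. Only a follow-up SD below the baseline SD would push it above a third.

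Three stronger readings are not supported:
- A reader might infer that β3 is invalid. It is a valid estimate of the difference in change.
- A reader might infer that adjustment should displace β3. Recruitment after allocation makes that a judgement about bias, not a free gain.
- A reader might infer that a third of the variance is being lost in this trial. That depends on a covariance and layout the plan has not settled.

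Separately, the power statement needs repair: of the variants tried, 0.80 at 0.55 came back only for a parallel-county change score under the Kronecker form. That is neither the current crossover nor the named SAS code.

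**What to change.** 1. Prespecify a baseline-adjusted model for each primary outcome: follow-up value on Int, the participant's baseline value and period, with county clustering suited to the crossover. Report it together with the Time-by-Int contrast. State in advance which of the two is primary and how a disagreement will be read.
2. State one covariance structure, since the Kronecker product and the SAS county intercept with compound-symmetric residual are not equivalent. Restate power for the chosen model in the two-period crossover, with the assumed numbers per county-period, degrees of freedom, retention and between-period county correlation.

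The cost is some SAP wording, a rerun of the power calculation and a second fitted model per outcome; no new data are needed. The adjusted estimate can carry a bias of about 0.65 of any persistent baseline difference, which is the reason for keeping Time-by-Int beside it.
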